## 10 Study Design

## 10.1 Trial Design

A randomised, single blinded, placebo controlled, cross-over trial of a LAIV. At day 0 participants will be randomised to either the early vaccine (EV) group, or the late vaccine (LV) group.

#### 10.1.1 Setting

Multicentre study conducted through academic and NHS clinical trials sites in primary and secondary care settings.

#### 10.1.2 Trial duration

Total duration of each participant will be 56 days from day 0 (the day of randomisation). The total trial period will be approximately 3 months.

### 10.1.3 Study groups

The study will consist of 2 groups of children who have been randomised to either the early vaccine (EV) or late vaccine (LV) arms of the trial.

## 10.1.4 Early Vaccine (EV)

Participants randomised to EV will receive the study intervention of 0.2ml Fluenz nasal spray (0.1ml per nostril) on day 0. At the follow up visit on day 28 they will receive 0.2ml of 0.9% saline placebo nasal spray (0.1ml per nostril). Their final follow up visit will be on 56 post randomisation.

## 10.1.5 Late Vaccine (LV)

Participants randomised to LV will receive 0.2ml of 0.9% saline placebo nasal spray on day 0 (0.1ml per nostril). At the follow up visit on day 28 they will receive the study intervention of 0.2ml Fluenz nasal spray (0.1ml per nostril). Their final follow up visit will be on day 56 post randomisation.

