### **Objectives and endpoints:**

Outcomes		
Primary		
Incidence of medically attended, physician- diagnosed wheeze or asthma or an illness for which the child was prescribed asthma medication.		
Secondary		
All medically attended adverse events		

**Brief Summary:** This study is a blinded, cross-over, randomised controlled trial of LAIV compared to placebo nasal spray in children aged 12 to 23 months. The primary outcome is medically attended wheeze in the four weeks following vaccination. To reduce the burden on GPs, study outcomes will be assessed by remote data extraction from electronic health records.

[figure not shown]
There will be two in-person study visits and one visit by digital questionnaire. At the first visit, participants will be consented, screened and randomised 1:1 to receive either LAIV or placebo nasal spray. Four weeks later at the second visit, basic safety information will be collected, and the participants will receive either vaccine or placebo (whichever they did not receive at the first visit). The final visit will be four weeks later and will be conducted via digital questionnaire to collect safety information. Recruitment will be enriched for children with a history suggestive of increased risk of wheezing, including a personal history in the child of eczema, bronchiolitis or viral induced wheeze.

**Number of Participants:** A total of 3000 children are expected to be randomised.

Interventions: All participants will receive live attenuated influenza vaccine (LAIV) (Fluenz, AstraZeneca) during the study. This is a live, attenuated, cold adapted influenza vaccine which is delivered as a nasal spray as 0.1ml solution per nostril. Participants will be randomised to either receive this at the first or second study visit. When not receiving LAIV they will receive 0.1ml per nostril of placebo, administered as normal saline via 1ml syringe and nasal atomiser device. Parents will be blinded to allocation.

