## 9 Objectives and Outcome Measures

Objectives	Outcome Measures	Timepoint(s)			
Primary					
To determine the safety and reactogenicity of LAIV in children	Episode of respiratory wheeze requiring medical attention diagnosed by a health practitioner	Day 0 to 28 following vaccination			
	Key secondary				
To assess safety of LAIV	Serious adverse events	Throughout the study			
	All medically attended adverse events	Throughout the study			

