## 9.1 Outcome ascertainment

Outcomes will be collected from routine GP medical records by the digital CRO, uMed. For medically attended wheeze, specific codes referring to a diagnosis of "Viral induced wheeze" and "Asthma" will be used, alongside findings of "Wheeze", and any new prescription for either Salbutamol or Ipratropium Bromide:

- 276191000000107 | Viral wheeze (disorder)
- 195967001 | Asthma (disorder)
- 56018004 | Wheezing (finding)
- 24612001 | Wheeze rhonchi (finding)
- 372897005 | Salbutamol (substance)
- 372518007 | Ipratropium (substance)

Whilst using codes of a finding of "wheeze" are most specific to the primary outcome, these codes are rarely used in practice and yield insufficient events. GP EPR data from a 3 month period indicates that, "Viral induced wheeze", and "Asthma" are the codes most commonly associated with wheezing. This

yields a population incidence of roughly 2% during a three-month period, in line with the power calculations for the study.

The primary outcome includes all events coded with a finding of "wheeze" together with the addition codes asthma/viral wheeze/salbutamol/ipratropium.

Additional medical attendances at locations other than the child's primary GP practice (e.g., hospital or other GP locations) will be determined using electronic diaries and solicited at follow up visits.

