## 14 Safety Reporting

## 14.1 Safety reporting window

Safety reporting for the trial will commence once the first participant is consented; and will end after the last participant has attended their final study visit for MAAEs and SAEs.

For individual participants the reporting period begins when consent is confirmed, in person, at the V1 visit, and ends after their final study visit.

All adverse events (AEs) that result in a participants' withdrawal from the study will be followed up until a satisfactory resolution occurs, or until a non-study related causality is assigned (if consent is provided).

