## 14.6 Procedures for Reporting Adverse Events

## 14.6.1 Medically attended AEs

A medically attended AE, is defined as any adverse event for which the participants' parents/legal guardians seeks medical attention for them either at hospital or from primary care. Participants' parents/legal guardians will be asked to record any medically attended AEs on their electronic diary. Medically attended AEs occurring up to 56 days post randomisation, will be directly solicited and reviewed at each study visit.

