## 27.2 Schedule of visits for the Late Vaccine (LV) cohort

Late Vaccine Group					
	D0	D28 (-3/+7)	D56 (+7)		
In person visit	X	х			
Digital Questionnaire			Х		
Consent	Х	х			
Collection of demographic data					
Medical History	X				
Concomitant medications	X	х	Х		
Weight	Х				
Randomisation	X				
Vaccination		х			
Placebo nasal spray	Х				
e-Diary information provided		x			
Study card provided	Х				
Diary Review			X		
Collection of SAEs, AESIs and MAAEs	To be reported at any time up to D56				

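### The protocol gives conflicting end points for second-period follow-up, so 1 to 7 of the 28 days after a second product given on D29 to D35 may go unsolicited

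*Protocol*

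**What the plan says.** Three kinds of end point appear in the Protocol.

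- **Day 56 from randomisation.** Section 10.1.5, for the late-vaccine (LV) arm: "Their final follow up visit will be on day 56 post randomisation". Section 10.1.4 gives the same day for the early-vaccine (EV) arm, and section 10.1.2 sets each child's participation at 56 days from day 0. Section 14.6.1: "Medically attended AEs occurring up to 56 days post randomisation, will be directly solicited and reviewed at each study visit". The schedules in section 3 and Appendix A give the collection period for SAEs and MAAEs as "To be reported at any time up to D56".
- **The final visit, whenever it occurs.** Section 14.1 says that the individual reporting period "ends after their final study visit". The schedules give that visit as D56 (+7), so D56 to D63.
- **The second visit or dose.** The brief summary in section 3, having described the second visit, says: "The final visit will be four weeks later and will be conducted via digital questionnaire to collect safety information". Section 9 sets the primary outcome at "Day 0 to 28 following vaccination". Section 15.2 censors undiagnosed children 28 days after vaccination in both periods, yet also describes the second period as Day 28 to Day 56.

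The schedules allow the second product on D28 (-3/+7), so D25 to D35.

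On sources, section 9.1 says: "Outcomes will be collected from routine GP medical records by the digital CRO, uMed". It leaves attendances elsewhere to the e-diaries and follow-up visits. Section 12.5.2 sends diary requests 7 and 14 days after each in-person visit.

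**The concern.** The three end points coincide only for a second product given on D28. After a later dose, a site that follows the D56 rule can close follow-up before the 28-day window has run out. An analysis window dated from the dose would not repair this for events found only by asking, because nobody would have asked.

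At stake is the completeness of the safety record late in the window. In LV the missing days follow LAIV; in EV they follow placebo. A hospital attendance for wheeze, or an SAE, on days 22 to 28 after the second product could go unsolicited, or could be treated as outside the stated period although section 9 counts those days.

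**Working it through.** **Inputs.** Second product on D25 to D35 and final contact on D56 to D63 (schedules, section 3 and Appendix A). Outcome window of 28 days (section 9). Diaries at 7 and 14 days after the visit (section 12.5.2). Placebo risk 0.9%, relative risk 2 and 2800 effective participants (section 15.1).

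**1. Days covered.** Covered days = min(28, last day covered − day of second product).

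| Second product | 28-day window ends | Covered if follow-up ends D56 | Covered if it ends D63 |
|---|---|---|---|
| D25 | D53 | 28 | 28 |
| D28 | D56 | 28 | 28 |
| D30 | D58 | 26 | 28 |
| D32 | D60 | 24 | 28 |
| D35 | D63 | 21 | 28 |

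The worst case is 56 − 35 = 21 days, leaving 7 of 28 (25%) uncovered. The +7 on the final contact is enough for full coverage (35 + 28 = 63), but nothing ties the contact to the dose date, so contact on D56 after a D35 dose complies with the plan.

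**2. Do the diaries fill the gap?** After a D35 visit the last diary request is on 35 + 14 = D49. From then on, solicited capture depends on the final contact alone.

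**3. Average shortfall.** Assume second visits fall evenly on the 11 days D25 to D35.

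- Every final contact on D56: the shortfall is 1 to 7 days for D29 to D35 and zero otherwise. Mean = (1+2+…+7)/11 = 28/11 = 2.55 days, or 2.55/28 = 9.1% of the window. Share of children affected = 7/11 = 64%.
- Final contacts spread evenly over the 8 days D56 to D63, independently of the dose date (a further assumption): the shortfalls over the 11 × 8 = 88 combinations sum to 1+3+6+10+15+21+28 = 84. Mean = 84/88 = 0.95 days, or 3.4%. Share affected = 28/88 = 32%.

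**4. Effect on the primary outcome.** Suppose that 10% to 40% of wheeze is attended outside the child's GP practice (assumption), that half of all events fall in the second period, and that the hazard is constant. The share of all primary events lost is 0.5 × 0.091 × (0.10 to 0.40) = 0.5% to 1.8% with every contact on D56. With contacts spread, it is 0.5 × 0.034 × (0.10 to 0.40) = 0.2% to 0.7%.

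**5. Upper bound if every primary event after D56 were lost.** The plan's 2800 is reproduced by a two-sided, continuity-corrected comparison of 0.9% with 1.8% at 80% power: 2798 observations per treatment, each child contributing one to each. Power at 2800 per treatment without the correction is 83.1%. With even spread, the second period keeps 1 − 0.091 = 0.909 of its events under both treatments. The average risks become 0.9% × (1 + 0.909)/2 = 0.859% and 1.8% × (1 + 0.909)/2 = 1.718%. Their ratio is still 2, and power is 81.3%. If every second visit were on D35, the risks would be 0.7875% and 1.575%, with power 77.9%.

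**The case against.** The strongest reply is that days 28 and 56 are nominal labels. Section 12.5 says that each visit has a time-point and a window. The +7 on the final contact matches the +7 on the second visit, so the schedule can accommodate the latest dose, and the D56 in the collection row can be read as the label of a visit that may take place up to D63. This stands as far as it goes: the schedule permits full coverage. It does not require it, and section 14.6.1 names 56 days from randomisation outright, so even a D63 contact leaves D57 to D63 outside that stated period.

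A second reply is that other routes stay open. GP extraction (section 9.1) has no stated D56 cut-off, nor does the line for reporting hospital admissions (sections 12.5.2 and 14.7), and section 16.2 mentions diary data for up to 28 days after administration. The first two stand and narrow the gap to events that depend on being asked about. The diary statement is a maximum and does not add a prompt after day 14.

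A reader might infer that every LV child dosed on D35 has only 21 days of follow-up, or that the trial is biased against finding harm from LAIV. The documents support neither. Contact on D63 gives all 28 days. EV children have the same gap after placebo, so both treatments lose a similar share of second-period days.

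**Conclusion.** The contradiction is real and should be resolved. Followed literally, section 14.6.1 and the schedules leave 1 to 7 post-dose days unsolicited and outside the stated period for a child in either arm dosed on D29 to D35 and contacted on D56. The worst case is 21 of 28 days covered. The mean shortfall lies between about 1 and 2.5 days under the two assumed patterns of final contact, both with second visits spread evenly; actual visit dates could give other values.

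The cost falls mainly on SAEs, MAAEs and wheeze attended away from the child's own practice. GP-recorded primary events are not necessarily lost, and the expected relative risk is little changed. The 64% of second doses that fall short of 28 days by D56 should not be read as the share of children losing data: that holds only if every final contact takes place on the earliest permitted day.

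**What to change.** Adopt one rule for data collection. Issue the final questionnaire no earlier than the later of D56 and day 28 after the actual second administration, and collect SAEs and MAAEs through that contact. Replace the two D56 limits (section 14.6.1 and the schedules), and bring sections 3, 10.1.2, 10.1.4, 10.1.5, 14.1, 15.2 and Appendix A (27.1 and 27.2) into line. In section 15.2, define the second period by the date of the second administration, as its censoring rule already does.

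The cost is amendment wording and one changed trigger date for an automated questionnaire, with no extra visit. The earliest contact stays within D56 to D63, because the latest second product gives 35 + 28 = D63. For late second visits the response window may have to run a few days past D63. Keeping a full 7 days after a D35 dose would take it to D70, so the amendment should state the limit.

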## 11 Participant Identification

## 11.1 Trial Participants

Participants will be children aged 12 months to 23 months. Comorbidities of clinical definition mild/moderate/well controlled will be permitted.

Children with a formal personal medical history of previous wheeze will specifically be invited to take part.

#### 11.2 Inclusion Criteria

- Aged between 12 months up until one day before their second birthday.
- Parent/legal guardian is willing and able to give written informed consent for participation in the trial.
- In good health as determined by a trial clinician. Participants may have well controlled or mildmoderate comorbidity, specifically including a personal history of eczema, bronchiolitis or viral induced wheeze
- In the Investigator's opinion, is able and willing to comply with all trial requirements.
- Willing to allow their General Practitioner and consultant, if appropriate, to be notified of participation in the trial
- Willing to allow investigators to discuss the volunteer's medical history with their General Practitioner and access all medical records when relevant to study procedures.

#### 11.3 Exclusion Criteria

The participant may not enter the trial if ANY of the following apply:

- Previous receipt of an IM seasonal influenza vaccine
- Receipt of any investigational vaccine other than the study intervention within 30 days before
  and after each study vaccination.
- Living in close contact with someone with a severely weakened immune system.
- Administration of immunoglobulins and/or any blood products within the three months
  preceding the planned administration of the vaccines.
- Children eligible for annual influenza immunisation according to the national NHS programme, including those with any confirmed or suspected immunosuppressive or immunodeficient state; asplenia; recurrent severe infections and use of immunosuppressant medication within the past 6 months, except topical steroids or short-term oral steroids (course lasting ≤14 days).

- History of allergic disease or reactions likely to be exacerbated by any component of study
  vaccines (e.g. hypersensitivity to gentamicin, gelatin, or other ingredients of Fluenz). Allergy
  to egg is only a contraindication if the participant has previously had anaphylaxis to egg.
- Any history of anaphylaxis.
- Current diagnosis of or treatment for cancer
- Any other significant disease, disorder or finding which may significantly increase the risk to
  the volunteer because of participation in the study, affect the ability of the volunteer to
  participate in the study or impair interpretation of the study data.
- Severe and/or uncontrolled cardiovascular disease, respiratory disease, gastrointestinal
  disease, liver disease, renal disease, endocrine disorder and neurological illness, defined
  broadly as currently requiring frequent hospital/specialist input or recently resulting in
  hospital admission, or as determined by the investigator (mild/moderate well controlled
  comorbidities are allowed).
- History of active or previous auto-immune neurological disorders (e.g. Guillain-Barre syndrome, transverse myelitis).
- Scheduled elective surgery during the trial
- Children receiving salicylate therapy (i.e., aspirin)
- Participants who have received an investigational product, or participated in another research trial involving an investigational product in the past 12 weeks or 5 half-lives after the last IMP dose (whichever is longer) before the first dose of study treatment.
- Parent or guardian has insufficient level of English language to undertake all study requirements in opinion of the Investigators except where translation has been able to be provided and is available.

## 11.3.1 Temporary exclusion criteria

If at Visit 1 Screening & Vaccination the volunteer has any of the following, they will not be enrolled that day.

- Acute respiratory illness with or without wheeze (moderate or severe illness with or without fever)
- Fever (oral temperature greater than 37.8°C)
- Active wheezing at the time of dosing/randomisation (including use of bronchodilators within the past 72 hours).

They may be considered for enrolment later in the trial if they recover in sufficient time.

## 12 Trial procedures

## See table in appendix A

#### 12.1 Recruitment

#### 12.1.1 Volunteer Identification

Potentially eligible participants will be identified via participating sites as children registered to GP practices within the age range of 12 to 23 months, and will be contacted via email/text message to inform them about the study and invite them to participate via approved materials.

Children aged 12–23 months will be identified by running a secure, pseudonymised query of participating GP practices' EMIS/TPP systems against the trial's inclusion/exclusion criteria within uMed's ISO-27001-certified AWS London environment. Before any invitations are sent, records will be cross-checked against the NHS National Data Opt-Out register to exclude those who have opted out of research contact. The resulting eligible list will then be approved by the GP practice. Once approved, parents or legal guardians will be sent SMS or email invitations—via uMed's platform— on behalf of their GP practice.

Volunteers may be recruited by use of an advertisement +/- registration form formally approved by the ethics committee and distributed or posted in the following places:

- From General Practitioner databases (including Child Health Information Services (CHIS)) by direct email or via use of uMed system.
- On institutional websites where information will be given and the volunteer information sheet will be downloadable or sent to the volunteer upon request
- In public places, including buses and trains, health centres, GP practice waiting rooms etc. with the agreement of the owner / proprietor
- In newspapers or other literature for circulation
- On radio via announcements
- On a website operated by our group or with the agreement of the owner or operator
- As a post on social media accounts including, but not limited to X, Facebook, Threads or other social media account owned and operated by the study research groups
- By email distribution to a group or list only with the express agreement of the network administrator or with equivalent authorisation
- By email distribution to individuals who have already expressed an interest in taking part in any clinical trial at the databases held at study sites.

- On stalls or stands at exhibitions or fairs
- Via presentations (e.g. presentations at lectures or invited seminars)
- Via PIC sites and other NHS databases local to sites

Volunteers parents/legal guardians will be sent a copy of the participant information sheet in response to requests for further information. Volunteers parents/legal guardians will be given a minimum of 24 hours to review the documentation where possible, prior to attending a screening visit. Sufficient time should be given prior to taking informed consent.

Recruitment will be enriched for participants with a history which might indicated a higher risk of wheezing illnesses, including:

- Personal medical history of wheeze or bronchiolitis
- Personal medical history of eczema

## 12.2 Screening and Eligibility Assessment

#### 12.2.1 Informed Consent

The study will obtain **legally valid informed consent from the parent or legal guardian** of each participant in accordance with:

- ICH-GCP E6(R2) section 4.8
- UK SI 2004 No.1031 (as amended), regulations 28–31
- MHRA "Remote and Electronic Consent" guidance (2020)
- HRA "Electronic Consent (eConsent) Guidance" (2018)
- UK GDPR and Data Protection Act 2018 (secure processing & audit trail)

The **primary route** will be fully compliant **electronic consent (eConsent)** delivered via the uMed platform; an equivalent **face-to-face consent** pathway is available on request.

## Step 1 – Digital Pre-screen Survey

- Parents receive an SMS or e-mail invite containing:
  - o short study introduction.
  - link to an online pre-screen (≤15 questions).
- If inclusion/exclusion criteria are met, the system displays the full **Participant Information Sheet (PIS)** and advances to eConsent.

### Step 2 - eConsent Workflow

- 1. PIS is presented in **plain language**, with expandable "More Info" sections, audio narration and large-print toggle.
- 2. The parent confirms identity (DOB of child + mobile OTP).
- 3. Mandatory understanding checks (≤4 quiz questions) guard against incomplete comprehension (GCP 4.8.11).
- 4. Electronic signature captured (typed name + date/time stamp + IP address).
- 5. **Tamper-proof PDF** of signed form is auto-e-mailed to the parent and filed in the site eISF; investigator signs the countersignature section at or before first visit.
- 6. The eConsent platform is **validated**, **Part-11-style** (audit trail, role-based access, version control) and hosted in the UK.

